4.3.2 Tracheal aspirate collection

Following bedside review of the collection procedures, nursing or respiratory staff will collect all tracheal aspirates in a standardized manner under the direct (in-person) guidance of a study team member. Our research team has extensive experience coordinating endotracheal sample collection for microbiome and cytokine analyses. In most cases, the timing of tracheal aspirate collection for research can be planned by the investigative and nursing teams to coincide with routine, clinical suctioning of the endotracheal (ET) tube. However, if the collection of a tracheal aspirate sample must occur at a set time (e.g., timed after an inhaled tobramycin dose) and routine clinical suctioning will not occur at that time, a research only collection will be performed. Clinical and research suctioning of the endotracheal tube will be performed as described in the paragraph below. In the CHOP N/IICU, infants with BPD who are receiving invasive mechanical ventilation undergo routine endotracheal suctioning several times per day. Most undergo clinical suctioning at least every 3 hours, and often more frequently (as much as every 20-30 minutes) owing to the high secretion burden in infants with GNR bacteria in the airways.

Tracheal aspirate samples will be collected by advancing a suction catheter just proximal to the end of the ET tube (length of ET tube is indicated at the bedside for all intubated infants). Tracheal secretions will be aspirated into a sterile Lukens trap. After tracheal secretion collection and removal of the suction catheter from the ET tube, the suction catheter will be cleared by aspiration of 1mL of sterile 0.9% saline (note: saline should not be instilled directly into the ET tube). This is the standard clinical procedure used to collect airway samples in the CHOP N/IICU. A minimum of 0.5mL of tracheal fluid will be collected - resulting in a total of approximately 1.5mL of fluid in the Lukens trap after flushing the suction catheter with 1mL of saline. In our experience, this procedure provides sufficient sample recovery for the specified analyses (see sections 5.1.2 and 5.1.3) and is consistent with tracheal aspirate volumes collected in prior studies.73-75 If less than 0.5mL of tracheal aspirate is recovered after a single suctioning, tracheal suctioning will be repeated at least 1 hour later, at the time of the next clinical suctioning. Of note, saline lavage is not performed prior to ET tube suctioning as this does not result in greater recovery of mucous material in infants and may adversely affect clinical stability.⁷⁶ A sterile (new) suction catheter will be used for all microbiological sampling as per unit protocol. Tracheal aspirate samples for tobramycin assays may be collected with a new suction catheter or the existing in-line suction catheter.

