2.2 Secondary Objectives

The secondary, exploratory objectives are to:

• Evaluate the association between the dose of inhaled tobramycin, plasma tobramycin pharmacokinetics, and peak tracheal aspirate tobramycin levels.

- Compare the change (pre vs. post study) in tracheal aspirate pathogenic bacterial colony forming unit (CFU) counts measured by high resolution culture, (1) between participants in the phase 1 trial and untreated infants in the observational cohort, and (2) between trial participants stratified by the administered dose of inhaled tobramycin.
- Compare the longitudinal change in measures of administered respiratory support (FiO₂, ventilator mean airway pressure, and respiratory severity score) during the 14-day study period, (1) between participants in the phase 1 trial and observational cohort and (2) between trial participants stratified by the administered dose of inhaled tobramycin.
- Compare changes (pre vs. post treatment) in tracheal aspirate cytokine levels, neutrophil/WBC ratio, and patterns in the airway microbiome, stratified by the administered dose of inhaled tobramycin.
- Change in the following measures of hypoxemia (SpO₂<80%): Intermittent hypoxemia (events lasting 10s-3min), prolonged hypoxemia (events lasting >1min), and daily proportion of time in hypoxemia
- Compare the longitudinal change in dynamic lung compliance, airway resistance, peak expiratory flow, and CO₂ elimination during the 14-day study period, (1) between participants in the observational cohort and phase 1 trial and (2) between trial participants stratified by the administered dose of inhaled tobramycin.

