Tracheal aspirate samples used for the measurement of tobramycin levels will be collected at the following times: (1) a single tracheal aspirate will be collected on days 4, 10, and 14, 11-hours after completion of the 8th, 20th, and 28th doses respectively; and (2) 5 samples will be collected on trial day 7, approximately 1-hour, 3-hours, 6-hours, 9-hours, and 11-hours after completion of the 14th tobramycin dose (see section 4.3) Tracheal aspirate drug levels will be measured in the laboratory of the University of Florida College of Pharmacology (see section 5.1.3). Tracheal aspirate drug levels will be concentrations needed to overcome the minimum inhibitory concentration necessary to kill 90% of detected bacterial isolates (MIC₉₀).^{90,91} Longitudinal change in tracheal aspirate levels will be modeled as part of the PK analyses. Correction for serum urea levels will be performed.

- Longitudinal change in the following respiratory support measures during the 14-day study period:
 - Fraction of inspired oxygen (FiO₂)
 - Ventilator mean airway pressure (MAP)
 - Respiratory severity score (MAP x FiO₂)

FiO₂ and mean airway pressure (MAP) are established clinical measures of respiratory disease severity. They characterize the amount of respiratory support (supplemental oxygen and positive airway pressure) required to maintain cardiorespiratory stability in infants receiving invasive respiratory support. The respiratory severity score (RSS) is a

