7.1.3 Dosing

This phase 1, dose escalation trial will investigate up to 4 different dosages of tobramycin solution for inhalation: 78mg, 150mg, 216mg, and 300mg. Each dose will be administered every 12 hours. For administered doses less than 300mg, the investigational pharmacy at CHOP will draw-up the appropriate volume from the 300mg/5mL tobramycin inhalational solution, USP ampule (i.e., 78mg = 1.3mL; 150mg = 2.5mL; 216mg = 3.6mL) using a single 3mL syringe (which indicate 0.1mL increments) or 5mL syringe (which indicate 0.2mL increments) as appropriate. The measured drug dose will then be diluted with sterile normal saline to produce a solution for aerosolization totaling 5mL. This will ensure that the same volume of liquid is aerosolized at each dosage level. All reconstituted drug product will be stored for not more than 4 hours at room temperature or 24 hours under refrigeration prior to administration.

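### The low-volume repeat rule in section 4.3.2 has no exception for timed tobramycin-level aspirates, so a low-yield 11-h sample can be retaken at or after the next dose and a low-yield 1-h sample at 2 h or later

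*Combined protocol and SAP*

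**What the plan says.** Section 4.3.2 sets one collection procedure for tracheal aspirates. On volume it says "A minimum of 0.5mL of tracheal fluid will be collected". On shortfall it says "If less than 0.5mL of tracheal aspirate is recovered after a single suctioning, tracheal suctioning will be repeated at least 1 hour later", and it places that repeat "at the time of the next clinical suctioning".

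The same section anticipates samples that must be taken at a fixed time after a dose. If routine suctioning does not fall then, "a research only collection will be performed". How that collection is done is referred onward: "Clinical and research suctioning of the endotracheal tube will be performed as described in the paragraph below". The paragraph referred to is the one with the repeat rule. It mentions tobramycin-assay samples once, to allow the in-line catheter to be used for them.

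The timed drug-level aspirates are set out in Table 5 (footnote d) and section 5.3. There are five on day 7, at about 1, 3, 6, 9 and 11 h after the 14th dose. There is one on each of days 4, 10 and 14, "11-hours after completion of the 8th, 20th, and 28th doses respectively". Section 7.1.3 gives the interval: "Each dose will be administered every 12 hours".

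The levels serve a secondary objective in section 2.2, relating dose to "plasma tobramycin pharmacokinetics, and peak tracheal aspirate tobramycin levels". They are also used in the comparison with target concentrations and in the PK work (sections 5.3, 6.3.3 and 6.3.4).

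**The concern.** A drug level means something only in relation to the time since the dose. The repeat rule suits culture, cytokine and cell-count samples, where an hour or more matters little. Applied to a timed drug-level sample, it moves the sample to another point of the dosing interval, and for the 11-h samples that point is the next dose or later.

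The plan gives no sampling window beyond approximate times. It does not say whether a low-volume first sample is kept, pooled or discarded, and it does not state that actual aspirate times are recorded. A late retake could therefore enter the dataset under its nominal time. At stake are the peak tracheal level by dose, the comparison with target concentrations, and the correlation of tracheal with plasma levels. Section 6.3.4 estimates the plasma level at the time of aspirate sampling from a log-linear decline between peak and trough; an aspirate taken after the next dose lies outside that decline.

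**Working it through.** **Inputs.** Repeat delay of at least 1 h, at the next clinical suctioning (4.3.2). Clinical suctioning at least every 3 h for most infants (4.3.2). Sampling times 1, 3, 6, 9 and 11 h (Table 5 footnote d; 5.3). Dosing interval 12 h (7.1.3). Full course 28 doses (4.7.2); check: 14 × 24 / 12 = 28. The documents give no airway half-life; 2 to 4 h is assumed here to show a range.

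**Step 1: when the retake falls.** Earliest retake = scheduled time + 1 h. If clinical suctionings are at most 3 h apart, one may fall just short of the 1-h mark and the next up to 3 h after it, so the latest retake is just under scheduled time + 4 h.

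| Scheduled | Retake window |
|---|---|
| 1 h | 2 to <5 h |
| 3 h | 4 to <7 h |
| 6 h | 7 to <10 h |
| 9 h | 10 to <13 h |
| 11 h | 12 to <15 h |

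A late retake of the 1-, 3-, 6- or 9-h sample may run into the next scheduled one.

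**Step 2: the 11-h samples against the dosing clock (hours from dose 1).** Dose n is given at 12(n − 1).

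| Day | Dose | 11-h sample | Earliest retake | Next dose due |
|---|---|---|---|---|
| 4 | 8 | 95 | 96 | 96 |
| 7 | 14 | 167 | 168 | 168 |
| 10 | 20 | 239 | 240 | 240 |
| 14 | 28 | 335 | 336 | none |

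Three of the four 11-h samples can be retaken at or after a dose. Day 14 cannot, because dose 28 is the last. If times run from completion of the dose, as section 5.3 has it, the retake falls later still by the nebulization time.

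**Step 3: size, assuming simple exponential decline with half-life h.**

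- Retake at 12 h, before the dose. Difference from the 11-h level = 1 − 2^(−1/h): 29% for h = 2, 16% for h = 4.
- Retake at the new peak, analysed as an 11-h value. Ratio = 2^(11/h): 2^5.5 = 45 for h = 2, 2^2.75 = 6.7 for h = 4. This does not depend on the peak concentration.
- 1-h sample retaken d hours late. Understatement = 1 − 2^(−d/h). For d = 1: 29% (h = 2) to 16% (h = 4). For d = 3: 65% to 41%.

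**Step 4: dilution of low-volume samples.** The catheter is cleared with a fixed 1 mL of saline, so dilution = (V + 1)/V for recovered volume V: 3-fold at 0.5 mL, 6-fold at 0.2 mL, 11-fold at 0.1 mL. Without correction, a 0.2 mL sample reads 6/3 = 2 times lower than a 0.5 mL sample of the same fluid, and a 0.1 mL sample 11/3 = 3.7 times lower.

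**Step 5: day 4, a separate point.** Table 5 places both the blood draw and the aspirate after the 7th dose. Its footnote d and section 5.3 time the aspirate to the 8th. The 11-h points are 72 + 11 = 83 h and 84 + 11 = 95 h, which are 12 h apart.

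**The case against.** The strongest reply is that the rule may seldom be triggered. Section 4.3.2 describes a high secretion burden, suctioning as often as every 20 to 30 minutes in some infants, and sufficient recovery in the team's experience. Timed samples have their own provision for a research-only collection, under in-person guidance from the study team. Because the repeat is tied to clinical suctioning, one could read it as never meant for set-time samples. Nothing says that a late retake will be labelled an 11-h value, and section 6.3.4 presupposes that aspirate times are known. The endpoints are exploratory, and the aspirate drug levels do not inform clinical decisions.

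Much of this stands, and it limits the size of the problem. It does not remove the conflict. The research-only provision secures the first attempt only, and it sends the reader to the paragraph that holds the repeat rule. That paragraph relaxes the catheter requirement for tobramycin-assay samples but not the repeat.

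Assaying a small on-time sample also has a real cost. Step 4 shows that dilution can distort an uncorrected level by as much as a late peak sample does (a 16-65% loss is about 1.2- to 2.9-fold), and section 5.1.5.1 calls the need for dilution correction uncertain. The fix has to deal with this.

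A reader might also infer three stronger things that the documents do not support:

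- That the primary safety endpoint is compromised. Its trough is a serum level from a blood draw, to which the rule does not apply.
- That airway troughs will generally be overstated 7- to 45-fold. This needs a low yield, a dose given before the retake, sampling at the new peak, and analysis as an 11-h value, all under an assumed half-life.
- That low yield marks infants who responded to treatment. Nothing in the documents links the two.

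**Conclusion.** The concern holds in a limited form. As written, section 4.3.2 conflicts with the sampling schedule in Table 5 and section 5.3. A low-yield 11-h aspirate on day 4, 7 or 10 is retaken at or after the time the next dose is due, and a low-yield 1-h aspirate at 2 h or later. The plan does not call the 1-h aspirate the peak, but no earlier one is available for the peak tracheal level objective.

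The effect is confined to low-yield samples, of unstated frequency, and to exploratory airway-level and PK analyses. Under the assumed half-life of 2 to 4 h, the error in an 11-h value is small if the 12-h retake precedes the dose (about 16-29%) and large only if it follows it (worst case about 7- to 45-fold). The clock arithmetic needs no assumption beyond the stated schedule; the percentages and ratios rest on the half-life. The rule should be corrected because the remedy is cheap.

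The day-4 mismatch between the 7th and 8th dose is a separate contradiction and adds no weight to this one.

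**What to change.** In section 4.3.2, exempt aspirates timed for tobramycin level from the delayed repeat, and add:

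- Keep the on-time sample and assay it where the laboratory's minimum volume allows (the documents do not give one); otherwise record it as missing.
- Record the recovered volume and the actual time since the dose for every drug-level aspirate.
- Flag samples under 0.5 mL and analyse them with the urea correction already planned, because the fixed 1 mL flush dilutes them more.
- Do not analyse any aspirate taken after the next dose as an 11-h value.

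In section 6.3.4, state that the PK analysis uses actual times. Separately, reconcile Table 5 with its footnote d and section 5.3 so that the day-4 blood and aspirate refer to the same dose; which dose is for the sponsor to settle.

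The cost is protocol and laboratory-manual wording. No procedure is added, and some repeat suctioning is avoided. The downside is that a few timed samples will be missing, or more diluted and less precise.

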4.3.3 Respiratory mechanics measurements

Respiratory mechanics data will be recorded at 3 timepoints: study entry (day 0 for participants in the phase 1 trial, day 1 for participants in the observational cohort), on study day 7, and ≤48 hours after completion of the 14-day study period. Respiratory mechanics will be measured using a Philips Respironics NM3 respiratory profile monitor placed in-line with the ventilator circuitry. Each recording will last for up to 4 hours. The Respironics sensor will be placed between the Neoflow sensor, if present, or directly to the endotracheal tube if not, and the "y" connector of the ventilator tubing. This device is FDA approved for use in infants (510 (k) K091459). The Respironics NM3 continuously monitors several mechanical and physiological respiratory parameters including minute ventilation, dynamic lung compliance, airway resistance, peak expiratory flow, and carbon dioxide elimination. These data will be downloaded to a dedicated, password protected study computer following each recording session. Respiratory mechanics measurements will be timed to correspond with quiet sleep periods.

The Respironics NM3 monitor sensor adds a negligible amount of dead space to the ventilator circuitry (0.8mL, <3% of inspired tidal volume for eligible study participants) and has been successfully used without adverse effects in infant studies,^{77,78} including those conducted in the CHOP N/IICU (IRB 12-008686). The same procedure for collecting respiratory mechanics data will be used for infants enrolled in the phase 1 trial and those enrolled in the observational cohort.

4.3.4 Continuous pulse oximetry

Continuous peripheral oxygen saturation (SpO₂) measurements will be obtained beginning 24-48hr prior to initiating the study drug and continued throughout the 14-day study period using a Masimo Rad-G pulse oximeter. A 2-second averaging time and 2-second sample rate will be used for all oximeter recordings. These parameters provide a more reliable measurement of the number and duration of hypoxemic events compared to the oximeters used for clinical care, which employ longer averaging times and less frequent sampling. The study pulse oximetry probe may be placed on any extremity in accordance with unit policy. The study pulse oximeter used for routine clinical care. The study pulse oximeter will be used in addition to the probe and oximeter used for routine clinical care. The study pulse oximeter will be used for research purposes only. The study pulse oximeter will not have programmed alarms, however saturation data will be displayed to ensure the oximetry probe and oximeter are functioning properly. Raw data will be extracted from the pulse oximeter every 72 hours and stored on a single password protected CHOP workstation for cleaning and analysis. The oximeter data will not be provided to the clinical team.

4.4 Follow-up Phase

The medical records of each enrolled subject will be periodically reviewed until hospital discharge for the following information:

- Occurrence of adverse events that may be related to the investigational drug
- Weekly abstraction of respiratory support and microbiological data (including all culture results and use of any antimicrobials)
- Weekly abstraction of respiratory medication administration (drug name and class)
- Discharge review of respiratory support data, audiology screening results, medications prescribed for home use, and discharge disposition

For the infants enrolled in the phase 1 trial, tracheal aspirate samples will be collected at 2 separate time points during the follow-up phase (as shown in **Table 5**). The first time point will be within 48 hours of completing the last dose of inhaled tobramycin. The second time point will be 14 days after the last administered dose of inhaled tobramycin or on the day of tracheal extubation, if earlier. Two tracheal aspirate samples will be collected at each timepoint to obtain enough fluid from the respiratory tract to complete the described laboratory testing (one sample will be analyzed in the clinical laboratory– see section 5.1.3.3; and the second is used for research laboratory analyses – see section 5.1.3.1). For infants enrolled in the observational (non-treated) cohort, a single tracheal aspirate for high resolution culture will be obtained within 48 hours after study day 14, or at the time of extubation, if earlier. The procedures described in section 4.2.2 will be used to obtain these samples. The final respiratory mechanics measurements in both study cohorts be obtained \leq 48 hours after completing the 14-day study period.

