^a "Day 0" procedures to be completed ≤7 days prior to administration of the first study drug dose. The quantitative tracheal aspirate culture and cell count differential obtained during the screening phase will be used for the laboratory values. Prior to initiating study drug therapy, one additional tracheal aspirate will be collected for cytokine level measurements and 16s sequencing.

^b "Day 15" procedures to be completed ≤48 hours after administration of the last study drug dose

° Follow-up tracheal aspirate for quantitative culture will be collected 14 days after the last administered dose of inhaled tobramycin or on the day of planned tracheal extubation if earlier

^d Tracheal aspirate for tobramycin level measurements obtained on trial day 7 will be collected approximately 1hr, 3hr, 6hr, 9hr, and 11hr after drug administration. Samples collected on trial days 4, 10, and 14 will be collected approximately 11hr after administration of doses number 8, 20 and 28, respectively.

e Serum and blood tobramycin trough levels will be drawn concurrently, 11 hours after administration of the previous dose

^f Blood draws for comprehensive metabolic panels should be bundled with draws for tobramycin trough levels or other clinically ordered blood draws. Comprehensive panel to include a magnesium and phosphorus level on day 7 and 14.

^g Serum and blood tobramycin peak levels will be drawn concurrently, 1 hour after completion of the previous dose

^h Up to 6 blood tobramycin levels per infant will be drawn concurrent with clinically ordered blood draws.

ⁱ Weekly medical record review to assess for adverse events will take place until hospital discharge

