4.7.2 Addition of Trial Participants after Early Termination

Additional research subjects will be added to the phase 1 trial as per the 3+3 design (**Figure 8**). In addition, subjects who are removed early from the trial for reasons other than

a toxic response or safety concern related to the investigational drug will be replaced 1:1 if fewer than 14 *doses* of inhaled tobramycin were administered. Up to 2 subjects total and no more than 1 per dose level, who receive \geq 14 *doses* of inhaled tobramycin, are removed early from the trial for reasons other than a toxic response or safety concern related to the investigational drug, and do not meet criteria for any of the primary tolerability endpoints will inform progression through the 3+3 trial design *without requiring participant replacement*. This is supported by the available data which show that elevated serum tobramycin trough levels in infants and young children are typically observed within the first 7 days of inhalational administration during every 12-hour dosing.⁴⁸⁻⁵⁰ PK analyses in young children demonstrate similar serum tobramycin levels are obtained after 28 days and after 56 days of inhaled tobramycin use suggesting negligible serum drug accumulation or impaired renal function when initial levels are reassuring.²¹

At least 3 infants must receive the full 14-day treatment course (28 doses) of the dose that is ultimately defined as the maximum tolerated dose at the end of this trial. Participants will be added as needed to fulfill this requirement. If the 300mg dose level is completed in 3 participants and none show evidence of a toxic response, up to 3 additional infants will be enrolled to receive to receive 300mg. This will provide a more robust assessment of drug tolerability and PK. The trial will be stopped if 2 of the additional infants receiving 300mg (2 out of 5 or 2 out of 6) develop a toxic response. In that event, the 216mg dose will be considered the maximum tolerated identified in this study.

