6.3.3 Exploratory Secondary Safety and Efficacy Analyses

The exploratory secondary safety and efficacy endpoints listed in section 6.2 will be analyzed as described in **Table 7** (next page). In brief, all study data will first be summarized using standard descriptive statistics as appropriate based on data type and distribution. Assessments of change over time for all longitudinal secondary outcome data will first be assessed graphically, with and without stratification by the administered tobramycin dose. Next, paired t-tests or Wilcoxon sign rank tests will be used to compare

pre-trial baseline values to those recorded at later time points. Non-paired tests will be used to compare data baseline and subsequent data points between the infants in the phase 1 trial and observational (non-treated) cohorts.

	Values available for:			
Study outcome	Phase 1 trial cohort	Observational cohort	Statistical approach	
Secondary safety endpoints	Yes	Yes, for some endpoints	 Rates of the secondary tolerability endpoints will be summarized for each dose level. Descriptive, narrative details of these endpoints will also be provided as appropriate. Data on the rates of endotracheal tube obstruction, unplanned tracheal extubation, and audiology testing results will be compared between the trial and observational cohorts. Planned comparisons of audiology testing results are described in the Protection of Human Subjects document. 	
Secondary efficacy endpoints				
Negative TA culture for the target GNR	Yes	No	 Primary exploratory efficacy endpoint. Rates will be summarized for the trial cohort as a whole and stratified by drug dose level. 	
Change in TA GNR pathogen CFU	Yes	No	 Absolute (pre vs post) and relative change ([post trial – pre trial] / pre trial) in the target organism CFU/mL on the log₁₀ scale will be calculated for each phase 1 trial participant. Paired t-tests or Wilcoxon sign rank tests as appropriate will be used to compare pre- vs. post-trial absolute CFU/mL values for the whole cohort and stratified by drug dose level. 	
Tracheal aspirate tobramycin levels	Yes	No	 Values, stratified by drug dose, will be compared to established concentrations necessary to overcome the minimum inhibitory concentration needed to kill 90% of detected bacterial isolates (MIC₉₀).^{90,91} Values will also be used in our PK analyses. 	

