of the drug was delivered when the bias flow was set to 2L/min and 10.6% \pm 0.3% when the bias flow was set to 5L/min.¹¹⁴ The ventilators used in the CHOP N/IICU to support infants with BPD use a bias flow of either 2.5L/min when set to the pediatric mode (most common for the target study population) or 4L/min when set to the neonatal mode. Extrapolating the published bench study data^{114,115} to the mechanical ventilators employed in this phase 1 trial, without correction for additional loss owing to the smaller endotracheal tubes used in the study infants (3.5-4mm), we conservatively estimate that **11-13% of the aerosolized** drug will reach the respiratory tract of enrolled study subjects. Further loss of drug may occur prior to the alveolar/capillary interface owing to the narrow caliber of the airways in infants and tighter bronchial branching patterns in small children.¹¹⁶⁻¹¹⁹ Despite this drug loss, the available data indicate the range of tobramycin dosages under investigation in this study will yield a dose that results in sufficient antimicrobial levels to significantly reduce the respiratory load of the targeted pathogenic organisms. In a study evaluating tobramycin levels in the epithelial lining fluid obtained by bronchoalveolar lavage 30-45 minutes after treatment with 300mg of inhaled tobramycin administered by jet nebulization to 12 young children with CF (mean age 3.3 years, range 0.9 to 5 years), the tobramycin concentration was within the target range in 11 or 12 patients, with a mean value of 90 µg/mL.²⁶ This level is above the minimum inhibitory concentration of 2-4µg/mL necessary to kill 90% of pseudomonas isolates (MIC₉₀) in vitro and the necessary sputum levels of approximately 50µg/mL needed to effectively eradicate *P. aeruginosa* in the airway.^{90,91} Modern vibrating mesh nebulizers produce a 2-3 fold higher drug output than do jet nebulizers, suggesting similar respiratory drug levels may be reached at the lower drug doses under investigation in this study. 108,120,121

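### The first post-treatment culture has a 48-hour upper limit but no lower limit, so some specimens can still contain inhibitory tobramycin and bias the exploratory culture results toward the drug

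*Combined protocol and SAP*

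**What the plan says.** Section 4.4 sets the first follow-up aspirate: "The first time point will be within 48 hours of completing the last dose of inhaled tobramycin". Table 5 footnote b defines its Day 15 column the same way: "procedures to be completed ≤48 hours after administration of the last study drug dose". The synopsis, Table 1 footnote b and sections 3.1.4, 5.1.4.3 and 5.3 repeat the 48-hour upper limit. None gives a minimum interval, a neutralising step, or a link between the culture and the measured airway drug level. Section 4.7.1 asks for two aspirates after the final dose in infants who stop early, with no timing.

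A second culture is planned 14 days after the last dose in trial infants only. It moves to the day of extubation if that comes first.

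Airway drug levels are sampled separately on days 4, 10 and 14, "11-hours after completion of the 8th, 20th, and 28th doses respectively" (section 5.3).

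Table 7 labels a negative culture for the target organism "Primary exploratory efficacy endpoint" but does not say which of the two post-treatment cultures counts. It lists negative culture and CFU change as unavailable in the observational cohort. Section 2.2 makes the CFU comparison with that cohort an objective, and section 5.3 schedules cultures for it.

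On concentrations, section 7.1.4 reports from a study of 300 mg by jet nebulizer in 12 young children with CF that "the tobramycin concentration was within the target range in 11 or 12 patients, with a mean value of 90" µg/mL, 30-45 minutes after the dose. It continues: "This level is above the minimum inhibitory concentration of" 2-4 µg/mL for 90% of Pseudomonas isolates.

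**The concern.** A culture taken a few hours after the last dose may be plated from fluid that still contains tobramycin above the MIC. A negative or low-count result could then partly reflect drug acting in the specimen rather than organisms cleared from the airway.

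Such carry-over would act in one direction, toward apparent efficacy. If airway level rises with dose, so would the artefact, and it could imitate a dose response across 78-300 mg. Study drug cannot cause it in untreated infants, so any CFU comparison with them would be tilted as well.

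Section 5.3 treats the change in quantitative culture as a suitable surrogate for clinical benefit, and section 6.3.3 intends CFU analyses to guide subgroup choices in later randomized trials. If the interval since the last dose is not planned and recorded, the artefact may be hard to separate from a true effect afterwards.

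**Working it through.** The plan states no figure on this point, so there is none to reproduce. The check asks how long a specimen could stay above the MIC90.

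**Inputs from the documents**
- Airway level about 30-45 min after 300 mg: mean 90 µg/mL (section 7.1.4).
- MIC90, Pseudomonas only: 2-4 µg/mL (section 7.1.4).
- Dilution at collection: at least 0.5 mL of fluid made up to about 1.5 mL by a 1 mL flush (section 4.3.2), so about 3-fold and 90/3 = 30 µg/mL.
- Window: 0-48 h after the last dose.

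**Assumptions, not in the documents**
- Airway half-life 2-4 h, widened to 1-6 h.
- Single-exponential decline. Time runs from the 90 µg/mL measurement, so time since the dose is 0.5-0.75 h longer.

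**Formula:** time to reach the MIC = half-life × log2(C0/MIC).

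**Number of half-lives at 300 mg**
- Undiluted: log2(90/4) = 4.49 to log2(90/2) = 5.49.
- Diluted: log2(30/4) = 2.91 to log2(30/2) = 3.91.

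**Inhibitory period at 300 mg**

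| Half-life | Diluted, MIC 4 to MIC 2 | Undiluted, MIC 4 to MIC 2 |
|---|---|---|
| 1 h | 2.9-3.9 h | 4.5-5.5 h |
| 2 h | 5.8-7.8 h | 9.0-11.0 h |
| 3 h | 8.7-11.7 h | 13.5-16.5 h |
| 4 h | 11.6-15.6 h | 18.0-22.0 h |
| 6 h | 17.4-23.4 h | 27.0-33.0 h |

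For the diluted specimen with a half-life of 2-4 h, the range is 5.8-15.6 h, or 5.8/48 = 12% to 15.6/48 = 33% of the window. Over every row and both columns it is 2.9-33.0 h, or 6-69%.

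**At the 11-h drug-level aspirate.** Of the six diluted scenarios with half-lives of 2, 3 and 4 h, three are still above the MIC90. They end at 11.6, 11.7 and 15.6 h, so two are only just above.

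**By dose, if level is proportional to dose (diluted, half-life 2-4 h)**
- 78 mg: 30 × 78/300 = 7.8 µg/mL; 0.96-1.96 half-lives; about 2-8 h.
- 150 mg: 15 µg/mL; 1.91-2.91 half-lives; about 4-12 h.
- 216 mg: 21.6 µg/mL; 2.43-3.43 half-lives; about 5-14 h.
- 300 mg: 30 µg/mL; 2.91-3.91 half-lives; about 6-16 h.

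**Illustrative effect on the negative-culture rate.** Observed rate = p + (1 − p) × f × s, where p is the true rate, f the share of cultures taken in the inhibitory period and s the chance that growth is then suppressed. With p = 0.30, s = 0.5 and 24 infants:
- f = 0.25: 0.30 + 0.70 × 0.25 × 0.5 = 0.3875, about 2 extra negatives (24 × 0.0875 = 2.1).
- f = 0.50: 0.30 + 0.70 × 0.50 × 0.5 = 0.475, about 4 extra (24 × 0.175 = 4.2).

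These values of p, f and s are assumed and are not estimates for this trial.

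**Does the Day 15 label act as a lower limit?** No. The footnotes define it only as within 48 h of the last dose. With 12-hourly dosing, dose 28 falls 27 × 12 = 324 h, or 13.5 days, after dose 1. If dose 1 is given in the morning, dose 28 is given on the evening of day 14, and its 11-h aspirate falls on the morning of day 15.

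**The case against.** The strongest reply is that a missing lower limit is not evidence of false negatives. Suppression in the airway while drug is present is a real, if perhaps transient, drug effect. Carry-over also needs drug to act in the trap or on the plate, and the documents give neither plating dilution nor time to plating. That stands: the plan can produce the artefact, but nothing shows that it will.

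Four stronger readings are tempting and are not supported.

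- **A much longer inhibitory period.** Section 7.1.4 says "Modern vibrating mesh nebulizers produce a 2-3 fold higher drug output than do jet nebulizers", and a reader might multiply 90 by 3 to start from 270 µg/mL. That turns device output directly into airway concentration. The section itself infers only that lower doses may reach similar levels, and it expects 11-13% delivery before further losses in small tubes and airways.
- **The culture will be taken with the 11-h aspirate.** Section 4.3.2 favours collection during routine suctioning, so bundling is possible. But Tables 1 and 5 list the samples separately, and section 4.3.2 sets different catheter rules for them.
- **The cohort comparison is biased.** Whether that comparison will be made is unclear, because Table 7 and section 2.2 disagree. The pre/post analysis in treated infants is exposed either way.
- **All organisms are equally affected.** The MIC90 is for Pseudomonas. Section 3.4.3 admits seven organism groups, and eligibility does not require tobramycin susceptibility.

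The later culture is a partial safeguard. It has no counterpart in the observational cohort, can move earlier with extubation, and is not named as the endpoint culture. The endpoints are exploratory, which limits the consequence but does not remove the gap.

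**Conclusion.** The gap is certain: every statement of the first post-treatment culture allows 0-48 h. On the plan's own concentrations, an early specimen can hold tobramycin above the Pseudomonas MIC90 and bias the negative-culture and CFU results toward the drug. The bias would be greater at higher doses if airway levels scale with dose.

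The magnitude is not known. The range of about 6-16 h at 300 mg rests on an assumed 2-4 h half-life, a 90 µg/mL start carried over from young children with CF, and the 3-fold dilution. Half-lives of 1-6 h with undiluted specimens included widen it to about 3-33 h. The period is shorter at lower doses and less relevant for resistant isolates.

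A reader might infer that the design invalidates the efficacy data or touches dose escalation. It does neither: the primary safety endpoint and the 3+3 decisions do not use these cultures. This is a cheap improvement to exploratory endpoints that later trials will rely on.

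**What to change.** - In Table 1 footnote b, Table 5 footnote b, the synopsis and sections 3.1.4, 4.4, 5.1.4.3 and 5.3, give the first post-treatment quantitative culture a lower limit inside the existing window, for example 24-48 h after the final dose. A 24-h minimum covers the diluted 300 mg specimen up to a half-life of 24/3.91 = 6.1 h. It does not cover every undiluted case, so timing must still be recorded.
- Collect this culture separately from the 11-h drug-level aspirate, and record hours since last dose.
- Keep but flag samples that must be taken earlier because of extubation, early withdrawal or the start of a systemic antibiotic. In the last case, waiting would add systemic antibiotic exposure and replace one bias with another.
- State in Table 7 which culture defines the negative-culture endpoint. Report results with and without flagged samples, beside the later culture with its actual timing.
- Reconcile Table 7 with sections 2.2 and 5.3 on whether CFU is compared with the observational cohort.

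The cost is slightly less scheduling flexibility and a few flagged samples. No sample is added, the window is not extended, and treatment does not change.
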